6.5. Missing Data

All attempts were made to collect all data per protocol. Imputations will only be performed for missing daily diary data as it relates to the primary endpoint. Missing daily diary data for the primary endpoint will be handled as follows:

- Data that are missing after a subject has reached clinical resolution will not affect the primary time to event analysis and therefore will be ignored
- Subjects who drop out, are lost to follow-up, withdraw consent, or otherwise stop completing daily diary entries before clinical resolution will be censored on the day of their last completed diary
- Subjects with a gap in outcome data prior to clinical resolution will be handled depending on their last completed diary entry and their next completed diary entry:
 - If the last completed diary entry and the next completed diary entry have the same outcome (i.e., they are still symptomatic on both days or they have no symptoms on both days), then the gap will be imputed with the same outcome
 - If this imputation results in the subject being defined as having clinical resolution during this gap, their time to resolution will be the median of the interval
 - If the last completed diary entry and the next completed diary entry have different outcomes (i.e., the last one is symptomatic and the next one is asymptomatic, or vice versa), then the gap will be imputed with the symptomatic outcome (no resolution).

[Table 3](#) provides summary statistics (n, mean, median, standard deviation, minimum, and maximum) of the number of imputed diary days per subject given the above imputation rules and the number of overall missing diary days per subject. The above method will be considered the primary imputation method for the primary endpoint. In addition, a sensitivity analysis on the primary endpoint will be conducted using worst case scenario for subjects who drop out, are lost to follow-up, withdraw consent, or otherwise stop completing

daily diary entries before clinical resolution. These subjects will be censored at 180 days (i.e., assuming resolution of symptoms occurred after Day 180). [Listing 9](#) provides subject-level details for the number of diaries missed by week.

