11 STATISTICAL CONSIDERATIONS

11.1 Study Hypotheses

A formal hypothesis test is planned to compare nitazoxanide to placebo with respect to the primary efficacy outcome measure. The time from randomization until clinical resolution of Norovirus for at least 48 hours through 180 days will be compared between the two study arms.

The null hypothesis is that there is no difference in time until clinical resolution between study arms, with a two-sided alternative. The test for primary efficacy hypothesis will be conducted using a Log-Rank test at the 5% two-sided level of significance.

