 - If the last completed diary entry and the next completed diary entry have the same outcome (i.e., they are still symptomatic on both days or they have no symptoms on both days), then the gap will be imputed with the same outcome
 - If this imputation results in the subject being defined as having clinical resolution during this gap, their time to resolution will be the median of the interval
- If the last completed diary entry and the next completed diary entry have different outcomes (i.e., the last one is symptomatic and the next one is asymptomatic, or vice versa), then the gap will be imputed with a symptomatic outcome (no resolution)

The above method will be considered primary and additional methods such as worst case scenario or best case scenario may be explored as supportive analyses to assess robustness of results.

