4.4.3. Method of Assigning Subjects to Treatment Groups (Randomization)

Enrollment of subjects will be done online using the enrollment module of Advantage eClinical. Eligible subjects will be randomized and assigned in a 1:1 ratio to active nitazoxanide or placebo. The study will use a stratified, permuted block randomization scheme. Permuted block randomization is used to avoid the potential for serious imbalance in the number of subjects assigned to each group, an imbalance that can occur in the simple randomization procedures.

Stratification will be by:

- Duration of symptoms: onset of Norovirus-associated symptoms (diarrhea, nausea and/or abnormal appetite) < 14 days vs. \geq 14 days
- Transplant Type: solid organ vs hematopoietic stem cell transplant
- Age Range: pediatric (12-17 years) vs. adult \geq 18 years

The randomization list will be computer-generated by statisticians at the Statistical and Data Coordinating Center (SDCC) using a stratified, permuted block randomization scheme and is included in the enrollment module for the trial. Advantage eClinical will assign each subject to a treatment group after the demographic, duration of symptoms, transplant type, and eligibility data have been entered into the system.

Each site will have a supply of two 60cc identical blinded bottles pre-labeled with randomization numbers, each containing 30 tablets, sufficient to treat a subject with 56 doses. The two identical containers will be packaged in the same plastic bag. Once a subject is assigned a randomization number, the corresponding bottles will be distributed to the subject.

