5. SAMPLE SIZE CONSIDERATIONS

Sample size calculations assume a 50% reduction in the median duration of diarrhea for the nitazoxanide-treated group compared to those receiving placebo. The median diarrhea duration for the placebo group is assumed to be 135 days, while the median diarrhea duration for the treatment group is assumed to be 67.5 days. Given these assumptions, a sample size of 64 subjects in each arm (128 total) is required to achieve 90% power using the Log-Rank test. Accounting for a 20% attrition rate, final sample size will be 80 in each arm (160 total).

Though discouraged, the protocol allows for subjects in either study group to receive additional nitazoxanide after 28 days. Under the assumptions of treatment efficacy, additional treatment received by placebo subjects would reduce the median duration of symptoms for the placebo group to be closer to that of the nitazoxanide-treated group. It is assumed that subjects who would have the worst study outcomes (longest time to clinical resolution of diarrhea) will be the most likely to receive additional treatment. Subjects receiving additional treatment will be imputed as having the worst outcome (time to resolution censored at 180 days). Accounting for this imputation method, the power attained for the primary comparison was computed via simulation (R version 3.0.3). Estimated power is displayed in [Table 2](#), varying the proportion of subjects in each study group who receive additional treatment.

For example, if 15% of placebo subjects receive nitazoxanide, and 5-10% of subjects in the nitazoxanide-treated group receive additional treatment, the power is estimated to be 91.2%. Note that implausible scenarios (where substantially more nitazoxanide subjects receive additional treatment than do placebo subjects) have been omitted from the table.

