8.1.1. Supplemental and Sensitivity Analyses

The primary analysis will be repeated in the Per Protocol analysis population, where subjects who were not compliant with the diary and/or treatment will be excluded from the analysis. The tabular and graphical summaries described in the previous section will be replicated for this Per Protocol analysis ([Table 16](#), [Figure 4](#), and [Figure 7](#)).

Sensitivity analyses will be performed using the stratified Cox proportional hazards model on both the mITT population and PP population using the worst-case scenario imputation method for subjects who drop out, are lost to follow-up, withdraw consent, or otherwise stop completing daily diary entries before clinical resolution ([Table 17](#)). These subjects will be censored at 180 days. Kaplan-Meier curves for each treatment arm will be presented ([Figure 5](#)). Kaplan-Meier curves for each treatment arm and duration of symptoms strata will be displayed in [Figure 8](#).

The primary analysis will be repeated on the mITT population using the subgroups defined in Section [6.4](#) ([Table 18](#)). A sensitivity analysis will be performed using the stratified Cox proportional hazards model on the mITT population with stratification based on subjects with less than 2 missing diaries per week versus

those with 2 or more missing diaries per week ([Table 19](#)). Kaplan-Meier curves for each treatment arm and diary compliance strata will be presented in [Figure 9](#).

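### The 'worst case' dropout analysis censors unresolved dropouts in both arms at Day 180, so it does not bound the treatment effect and can move it in either direction

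*SAP*

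**What the plan says.** In the primary analysis (SAP 6.5, Protocol 11.4.3.1), a subject who stops completing the diary before resolution is censored on the day of the last completed diary.

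SAP 6.5 adds one sensitivity analysis for these subjects, called worst case: "These subjects will be censored at 180 days (i.e., assuming resolution of symptoms occurred after Day 180"). SAP 8.1.1 repeats it for Table 17, in the mITT and PP populations, with a stratified Cox model "using the worst-case scenario imputation method for subjects who drop out". Neither section distinguishes the arms. The Table 16 shell, which Table 17 follows, reports the hazard ratio as nitazoxanide to placebo with a confidence interval and a likelihood ratio p-value. The event is resolution, so a ratio above 1 favours nitazoxanide.

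Protocol 11.4.3.1 left the choice open: "worst case scenario or best case scenario may be explored as supportive analyses to assess robustness of results". The SAP takes up only the common rule. It plans no best case, arm-specific or tipping-point run.

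**The concern.** A worst-case analysis is normally read as a floor: if the effect survives it, missing data cannot explain the effect. That reading needs the missing outcomes filled in against the claim, so dropouts on active treatment fail and dropouts on control succeed. Here both fail. Each unresolved placebo dropout kept at risk to Day 180 lowers the placebo resolution rate and helps nitazoxanide. The direction of the run therefore depends on which arm loses more unresolved subjects, and the result can be better for nitazoxanide than the primary analysis.

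This is the only planned analysis that changes the assumed outcome of dropouts. Table 19 stratifies on missed diaries but leaves dropout censoring as it is. The PP population requires follow-up to resolution or to Day 180 (SAP 6.3.2), so unresolved dropouts are excluded from it and the rule has almost nothing to act on there.

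**Working it through.** **Inputs from the documents.** Protocol 11.1: "The test for primary efficacy hypothesis will be conducted using a Log-Rank test at the 5% two-sided level of significance". SAP 5 takes medians of 135 days on placebo and 67.5 days on nitazoxanide, and concludes that "a sample size of 64 subjects in each arm (128 total) is required to achieve 90% power using the Log-Rank test". Allowing for attrition of 20%, it plans 80 per arm, 160 in all. SAP 4.4.3: "Eligible subjects will be randomized and assigned in a 1:1 ratio to active nitazoxanide or placebo". Follow-up is 180 days. Enrolment stopped at 31 (SAP 6.6).

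**Assumptions.** Exponential times to resolution. Dropout by arm is not given, so pairs averaging the stated 20% are used, with dropout times uniform over 180 days and independent of outcome. The split of 31 is taken as 16 and 15.

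**Step 1: the plan's own figures.** With median m, P(resolved by Day 180) = 1 − 2^(−180/m): 0.603 for placebo, 0.843 for nitazoxanide, mean 0.723. The hazard ratio is 135/67.5 = 2.0.
- Schoenfeld: 4 × (1.960 + 1.282)² / (ln 2)² = 87.5, so 88 events; 88/0.723 gives 122 subjects.
- Freedman: 10.51 × (3/1)² = 94.6, so 95 events; 95/0.723 gives 132 subjects.
- The stated 128 lies between. At 128 subjects, 92.5 events give √(92.5/4) × 0.693 − 1.960 = 1.37, or 91.5% power. 64/0.8 = 80 per arm.

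The sample size is not in question.

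**Step 2: direction by hand, no true effect (both medians 135 days).** The average probability of still being unresolved at a uniform dropout time is [135/(180 ln 2)] × 0.603 = 0.653. With dropout risk d, the share lost before resolution is 0.653d. Under the SAP rule the share counted as resolved is (1 − d) × 0.603 + d × 0.347. At 10% nitazoxanide and 30% placebo:
- nitazoxanide 0.9 × 0.603 + 0.1 × 0.347 = 0.578
- placebo 0.7 × 0.603 + 0.3 × 0.347 = 0.526

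The implied ratio is ln(1 − 0.578)/ln(1 − 0.526), about 1.15, although the arms do not differ. At equal dropout risk the two shares are equal and the ratio is 1.

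**Step 3: simulation** (20,000 trials per setting; median Cox hazard ratio; unstratified log-rank test). No true effect, 64 per arm; the primary rule stays at 1.00 throughout:

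| Dropout risk %, nitazoxanide/placebo | Lost before resolution % | HR, SAP rule | False win for nitazoxanide (nominal 2.5%) | HR, SAP rule, 16 vs 15 |
|---|---|---|---|---|
| 20/20 | 13.1/13.1 | 1.00 | near nominal | 1.00 |
| 15/25 | 9.8/16.3 | 1.06 | 4.3% | 1.06 |
| 10/30 | 6.5/19.6 | 1.13 | 7.2% | 1.13 |
| 5/35 | 3.3/22.8 | 1.20 | 11.8% | 1.21 |
| 30/10 | 19.6/6.5 | 0.89 | below nominal | 0.88 |

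At 16 vs 15 and 10/30, the false-win rate is 4.6%, against 2.6% under primary censoring.

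**Step 4: true hazard ratio 2.0.** For nitazoxanide the average in Step 2 becomes [67.5/(180 ln 2)] × 0.843 = 0.456. The arm-adverse rule keeps nitazoxanide dropouts unresolved to Day 180 and counts placebo dropouts as resolved at the last diary.

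| Dropout risk %, nitazoxanide/placebo | Lost before resolution % | HR, primary | HR, SAP rule | HR, arm-adverse |
|---|---|---|---|---|
| 20/20 | 9.1/13.1 | 2.00 | 1.93 | 1.41 |
| 15/25 | 6.8/16.3 | 2.01 | 2.06 | 1.39 |
| 10/30 | 4.6/19.6 | 2.01 | 2.19 | 1.37 |
| 30/10 | 13.7/6.5 | 2.00 | 1.71 | 1.46 |

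Rows 15/25 and 30/10 are from runs at 80 per arm, except the SAP value at 15/25, which was 2.06 at both sizes. In the 10/30 row at 64 per arm, power is 89% under the primary rule, 95% under the SAP rule and 34% under the arm-adverse rule. With no true effect at 10/30, the arm-adverse rule gives 0.69.

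**The case against.** Several points on the other side are sound.

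- **The label is right at subject level, and the rule is written out.** SAP 6.5 says what is assumed. The fault lies in reading the run as a bound on the comparison.
- **Nothing was dropped against the protocol.** A reader might infer that the SAP breaches Protocol 11.4.3.1 by omitting the best case. It does not: both cases were optional there.
- **It is not the only missing-data check.** A reader might infer that it is. Table 19 and the PP repeat in SAP 8.1.1 also touch missing diaries and dropout, but neither changes what is assumed about dropouts in the mITT set.
- **More placebo losses do not always help nitazoxanide.** At 20/20 with a true effect, placebo loses 13.1% and nitazoxanide 9.1% before resolution, yet the hazard ratio falls from 2.00 to 1.93.
- **The simulation makes the primary rule unbiased by construction,** because dropout is independent of outcome. The SAP run asks a fair question: what if dropouts stay unresolved? That justifies keeping it, but does not make it a floor. The simulation also uses an unstratified log-rank test, where the SAP specifies a stratified Cox model with a likelihood ratio test.
- **The trial is small.** SAP 14.2 calls the analyses primarily descriptive, and Table 6 and Listing 2 will show early terminations by arm. But the Table 17 format still carries a hazard ratio, interval and p-value, and Table 6 does not say whether a termination came before resolution.

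**Conclusion.** The concern holds in this form: the run called worst case is a common non-resolution rule. It does not bound the treatment effect, and its direction depends on the balance of unresolved dropouts between arms. Under no effect the hazard ratio ranges from 0.89 (30/10) to 1.20 (5/35). With a true ratio of 2.0 it ranges from 1.71 (30/10) to 2.19 (10/30) in the settings shown.

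The direction follows from the rule itself. The sizes rest on exponential times, uniform non-informative dropout and assumed splits by arm, so they illustrate and do not predict. The documents do not support the stronger inference that this analysis is biased towards nitazoxanide in this trial: they do not say which arm lost more, and in two of the situations shown the rule is conservative. The primary analysis and the sample size are unaffected.

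**What to change.** 1. Rename the current run in SAP 6.5, SAP 8.1.1, Table 17 and Figures 5 and 8 as 'dropout counted as non-resolution in both arms'. Keep it.
2. Add one arm-adverse bound to the mITT part of Table 17: unresolved nitazoxanide dropouts censored at Day 180, unresolved placebo dropouts imputed as resolved just after their last diary. State that this is an extreme imputation, outside the diary definition of resolution in SAP 3.3 (two consecutive symptom-free entries), and is to be read only as a bound. It is not needed for PP.
3. Report beside it the number of dropouts before resolution in each arm.

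The cost is one model run, one label and one row of counts. The downside is severity: a true hazard ratio of 2.0 becomes about 1.4 at 20/20 dropout, so failing the bound does not show that the effect is absent. With 31 subjects it stays descriptive.

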6.6. Interim Analyses and Data Monitoring

The Data and Safety Monitoring Board (DSMB) planned to review and discuss study data when 25% (N=40), 50% (N=80), and 75% (N=120) of patients completed Day 60 of the study. All planned DSMB reviews were to include descriptive summaries and were not intended to serve as formal interim analyses. Blinded and unblinded reports on safety data through Day 60, Norovirus infection clinical adverse outcome through Day 180 along with available clinical and virologic efficacy data and study product nitazoxanide retreatment data were expected to be reviewed at each study milestone.

At the time of this SAP, the study was stopped after 31 subjects enrolled due to enrollment challenges. Even though the study never reached the first milestone (N=40 subjects), the DSMB completed an unplanned electronic review of the Open and Closed Safety and Summary Reports on 02 November 2020.

The halting rules did not utilize any statistical criteria and no formal hypothesis testing occurred for the safety or efficacy review; therefore, no adjustment for multiple testing will be performed.

A final review meeting will be conducted 6 to 8 months after clinical database lock to review the cumulative unblinded safety and efficacy data for the study.

6.7. Multicenter Studies

Data will be pooled across all clinical sites. Center effects are not anticipated because the sites are using standardized procedures for product administration and assessment of safety and efficacy endpoints.

6.8. Multiple Comparisons/Multiplicity

There is only one primary endpoint. No adjustments for multiple testing are planned.

7. STUDY SUBJECTS

7.1. Disposition of Subjects

[Table 9](#) will present a summary of the reasons that subjects were screened but not enrolled.

The composition of analysis populations, including reasons for subject exclusion, by treatment arm, is presented in [Table 7](#).

The disposition of subjects in the study will be tabulated by treatment group ([Table 6](#)).

A flowchart showing the disposition of study subjects, adapted from the CONSORT Statement, will be included ([Figure 2](#)). This figure will present the number of subjects screened, enrolled, lost to follow-up, and analyzed, by treatment group.

A listing of subjects who terminated from study follow-up or discontinued treatment and the reason will be included in [Listing 2](#).

7.2. Protocol Deviations

A summary of subject-specific protocol deviations will be presented by deviation category, type, and treatment group for all subjects ([Table 4](#)). All subject-specific protocol deviations and non-subject specific protocol deviations will be included in Appendix 3 as data listings ([Listing 3](#) and [Listing 4](#), respectively).

8. EFFICACY EVALUATION

All primary and secondary efficacy analyses will be conducted in the mITT and PP populations. Data will be summarized by treatment group with a column for each treatment in the order (Nitazoxanide, Placebo) and will be annotated with the total population size relevant to that table/treatment. Subgroups with less than five subjects per treatment group will be excluded from efficacy tables and figures. All efficacy variables will be listed by site, treatment group and subject, and when appropriate, by visit number within subject ([Listing 12](#), [Listing 13](#), [Listing 14](#), [Listing 15](#), [Listing 16](#), [Listing 17](#), [Listing 18](#), [Listing 19](#), and [Listing 22](#)).

8.1. Primary Efficacy Analysis

The primary efficacy outcome measure is the time from randomization to initial clinical resolution of Norovirus for at least 48 hours, assessed through 180 days, in each study arm. Clinical resolution will be assessed from the daily diary by the subject and will be defined as in Section [3.3](#).

The protocol calls for a formal hypothesis test to compare nitazoxanide to placebo. The null hypothesis is that there is no difference in time until clinical resolution between study arms, with a two-sided alternative. A stratified Log-Rank test at the 5% two-sided level of significance was planned to test the hypothesis, however, due to early closure of the study, the number of subjects is too small to use a Log-Rank test. Instead, a stratified Cox proportional hazards model will be used to compare treatment to control through Day 180 with respect to time to clinical resolution. Stratification is based on acute versus chronic symptoms at baseline. No pediatric subjects were enrolled in the study and only one hematopoietic stem cell transplant subject was enrolled in the study; therefore, the transplant type and age range strata will not be included in the final analysis.

The primary analysis will be performed in the mITT analysis population. Missing diary data will be imputed using the methods described in Section [6.5](#). The treatment hazard ratio estimate, 95% confidence interval and p-value from the likelihood ratio test will be presented ([Table 16](#)). The median time to clinical resolution and 95% confidence interval will be summarized by treatment arm and duration of symptoms. In addition, stratum-specific estimates of the treatment hazard ratio within each duration of symptoms strata will be presented. Kaplan-Meier curves for each treatment arm will be displayed in [Figure 3](#). [Figure 6](#) will present Kaplan-Meier curves for each treatment arm and duration of symptoms strata.

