11. OTHER ANALYSES

The protocol calls for a Log-Rank test at the 5% two-sided level of significance for the following outcome measures:

- Time to allograft rejection as per each center team.
- Time to graft loss as reported to UNOS.
- Time to death.
- Time to withdrawal from the study because of intolerance or drug related adverse events.

However, due to early closure of the study, the number of subjects is too small to use a Log-Rank test. Instead, a stratified Cox proportional hazards model will be used to compare treatment to control through Day 180. Stratification is based on acute versus chronic symptoms at baseline. No pediatric subjects were enrolled in the study and only one hematopoietic stem cell transplant subject was enrolled in the study; therefore, the transplant type and age range strata will not be included in the final analysis.

The analysis will be performed in the mITT analysis population. The treatment hazard ratio estimate, 95% confidence interval and p-value from the likelihood ratio test will be presented for each event ([Table 108](#)). The median time to event and 95% confidence interval will be summarized by treatment arm and duration of symptoms. In addition, stratum-specific estimates of the treatment hazard ratio within each duration of symptoms strata will be presented. Kaplan-Meier curves for each treatment arm will be displayed in [Figure 27](#), [Figure 28](#), [Figure 29](#), and [Figure 30](#). A listing of graft loss and rejection is presented in [Listing 29](#) and a listing of deaths is presented in [Listing 30](#).

The primary analysis will be repeated on the mITT population using secretor status as defined by phenotype and genotype, separately ([Table 48](#)). Individual secretor status data is presented in [Listing 19](#).

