14.2. Changes in Planned Analyses

It was originally planned that the study would enroll 160 subjects allowing for larger sample statistical methods to be used; however, due to early closure of the study only 31 subjects enrolled. Therefore, it is anticipated that many of these tests will no longer be valid. Many of the analyses from the protocol have been updated to employ small sample techniques and will be primarily descriptive.

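### Having 31 subjects is no reason to replace the log-rank test with a Cox likelihood-ratio test: the swap gains nothing for the primary endpoint and can overstate significance when few events occur

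*SAP*

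**What the plan says.** Protocol 11.4.3.1 tests the primary endpoint with a stratified log-rank test and reports median times by arm. SAP 8.1 acknowledges this ("A stratified Log-Rank test at the 5% two-sided level of significance was planned to test the hypothesis") and then sets it aside: "however, due to early closure of the study, the number of subjects is too small to use a Log-Rank test". The replacement reads: "Instead, a stratified Cox proportional hazards model will be used to compare treatment to control through Day 180". It adds that the hazard ratio, its interval and the "p-value from the likelihood ratio test will be presented". One stratification factor remains: "Stratification is based on acute versus chronic symptoms at baseline".

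The same reason and replacement appear in SAP 8.2 (time to first negative viral load), SAP 8.3 (exploratory time-to-event outcomes) and SAP 11 (allograft rejection, graft loss, death, withdrawal for intolerance or drug-related events), where it reads: "However, due to early closure of the study, the number of subjects is too small to use a Log-Rank test". SAP 14.2 describes the revisions as a whole: "Many of the analyses from the protocol have been updated to employ small sample techniques and will be primarily descriptive".

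For the exploratory time-to-event outcomes, including those now in SAP 11, Protocol 11.4.5 had already planned a log-rank test together with a Cox hazard ratio and 95% interval.

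**The concern.** If a sample is too small for the chi-square approximation behind the log-rank test, it is also too small for the one behind a Cox likelihood-ratio test. The likelihood-ratio test is not a small-sample technique in the sense SAP 14.2 claims. The SAP does use such techniques elsewhere: exact Wilcoxon tests in SAP 8.3 and 9.9, and Barnard's exact test in Table 50.

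Two things are at stake. The protocol's primary test is given up on a rationale that does not support the change. And where events are few, the substitute can give a nominally significant difference in an outcome such as death or graft loss on evidence that an exact test would call unremarkable.

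**Working it through.** **Inputs.** 31 subjects (SAP 6.6, 14.2); 1:1 allocation (SAP 4.4.3), taken as 16:15; medians 135 and 67.5 days (SAP 5); follow-up 180 days; two-sided 5%. Stratum sizes are not given, so 6/25, 12/19 and 15/16 were used. Event probabilities for the SAP 11 outcomes are not given, so 3% to 30% was used. Times are exponential, without ties or dropout in the null runs.

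**1. Same model, same approximation.** Let l(b) be the stratified Cox partial log-likelihood for the treatment coefficient b, with score U(0) and information V(0) at b = 0. The stratified log-rank statistic is U(0)²/V(0). The likelihood-ratio statistic is 2[l(b̂) − l(0)]. Both are referred to chi-square with 1 df. The identity is exact without ties and close with the usual tie approximations; the SAP names no tie method.

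**2. The plan's own figure.** Event probabilities by day 180 are 1 − 0.5^(180/135) = 0.603 and 1 − 0.5^(180/67.5) = 0.843, mean 0.723. Freedman's formula gives 95 events, and 95/0.723 = 131 subjects (66 per arm), against the plan's 128 (64 per arm). The Lachin-Foulkes formula gives 64.7 per arm. Simulated log-rank power at 64 per arm is 91.5%, against 91.3% in the first cell of SAP Table 2. And 128/0.8 = 160. The setting is reproduced.

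**3. Primary endpoint at 31 subjects.** In 30,000 null trials per setting (strata 6/25 and 15/16), the likelihood-ratio test rejects in 5.2% and the log-rank test in 5.4%, with about 19 events. If the acute stratum resolves quickly, the figures are 5.4 to 5.5% and 5.6 to 5.8%. Runs with strata 12/19 and 70% events give 5.6 to 5.8% and 5.8 to 5.9%. Power at the design effect is 36% against 36 to 37%.

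**4. Few events, by enumeration.** With equal risk sets, each of d events falls in either arm with probability 1/2. For three events, all in one arm:
- likelihood ratio: 2 × 3 × ln 2 = 4.16, p = 0.041
- log-rank: 1.5²/0.75 = 3.00, p = 0.083
- exact: 2 × (1/2)³ = 0.25

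| Total events | Likelihood-ratio size | Log-rank size |
|---|---|---|
| 1 or 2 | 0 | 0 |
| 3 | 25% | 0 |
| 4 | 12.5% | 12.5% |
| 5 | 6.25% | 6.25% |
| 6 | 3.1% | 3.1% |
| 8 | 7.0% | 7.0% |

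With one or two events the likelihood-ratio test cannot reject (2 × 2 × ln 2 = 2.77, below 3.84). In simulation with a 16:15 split, its size at exactly three events is about 21 to 24%. At seven events the enumeration gives 12.5% against 1.6%, but simulation with unequal, shrinking risk sets gives about 8 to 9% against 6 to 7%, so the simulated figure is the one to use there.

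**5. Few events, overall size by simulation (strata 6/25 and 15/16).**

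| Event probability | Expected events | Likelihood-ratio | Log-rank |
|---|---|---|---|
| 3% | 0.9 | 1.2–1.3% | 0.1% |
| 5% | 1.6 | 3.6–3.7% | 0.6–0.7% |
| 8% | 2.5 | 6.8% | 1.8–2.0% |
| 10% | 3.1 | 7.8–8.3% | 2.6–2.8% |
| 15% | 4.6 | 8.0–8.3% | 4.2% |
| 20% | 6.2 | 6.9–7.1% | 4.8–4.9% |
| 30% | 9.3 | 5.7–5.8% | 5.1–5.2% |

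Strata of 12/19 give 8.1 to 8.5% against 2.6 to 2.7% at 10%, and a likelihood-ratio size of 5.0% at 6%.

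**6. Non-finite hazard ratios.** The estimate is zero or infinite when exactly one arm has no events. At a 10% event probability that chance is 0.9^16 + 0.9^15 − 2 × 0.9^31 = 0.185 + 0.206 − 0.076 = 31%. At 6% it is 47%.

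**The case against.** The strongest reply is that nothing is harmed where it matters most. For the primary endpoint the two tests have the same error rate and power, the change is disclosed in every section concerned, and the Cox model adds a hazard ratio and interval that the protocol's primary analysis lacked. That is useful in a 31-subject trial the SAP calls mainly descriptive. All of this stands, but adding an estimate does not require dropping the test.

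The second reply concerns the sparse outcomes. A reader might infer that the likelihood-ratio test rejects too often whenever events are rare. It does not. The documents' own rates point to the low end: Protocol 2.1 reports 1 death and 3 graft failures related to the illness within a year among 67 solid organ recipients with Norovirus. Applied to 31 subjects, 1/67 and 3/67 give 0.5 and 1.4 expected events, below the inflated band. Protocol 9.1 gives one-year survival from 87.2% (liver) to 98.3% (kidney), and follow-up here is only 180 days. Overall inflation for death and graft loss is therefore not shown. For rejection and withdrawal the documents give no rate. What survives is the conditional risk: once three or more events occur, at event probabilities of 3 to 10%, the likelihood-ratio test rejects in 13 to 20% of null trials and the log-rank test in 2 to 5%.

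A reader might also infer that the swap creates the non-finite hazard ratios. It does not: Protocol 11.4.5 had already planned Cox hazard ratios for these outcomes. The efficacy mock-ups with Cox estimates (for example Tables 16, 18, 21, 23 and 29) carry a not-calculable instruction. Table 108 does not, and the fewer-than-five rule in SAP 8 counts subjects, not events, and covers efficacy tables and figures.

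**Conclusion.** The stated reason for abandoning the log-rank test is wrong. For the primary endpoint the fault stops there: an unnecessary departure from the protocol's test, with no measurable change in type I error or power. A reader might infer that the primary p-value is invalid or that the test was chosen to favour a result; neither the figures nor the documents support that.

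For the SAP 11 outcomes the likelihood-ratio p-value is anti-conservative at roughly 2.5 to 9 expected events, and markedly so at exactly three (about 22 to 25%). It cannot reject at one or two events, and its overall size is at or below 5% at event probabilities of 6% or less. These outcomes are exploratory, which limits the stakes. The asymptotic log-rank test is itself oversized at some counts (4, 5 and 8 by enumeration), so simply restoring it would not be a full remedy.

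The figures assume a chi-square reference (the SAP names no exact version), the 16:15 split, the assumed stratum sizes, exponential times and no ties. Event counts are the main unknown.

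**What to change.** - Delete the statement in SAP 8.1, 8.2, 8.3 and 11 that the sample is too small for a log-rank test.
- Keep the protocol's stratified log-rank statistic for the time-to-event outcomes, with a p-value from permuting treatment within the acute and chronic strata.
- Use the Cox model for the hazard ratio and interval only.
- In Table 108 report event counts, Kaplan-Meier curves and the permutation p-value, and show the hazard ratio as not calculable when either arm has no events.

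The cost is SAP wording and a few lines of code. In simulation the permutation test's size is 4.8 to 5.3% for the primary endpoint and 3.2 to 3.5% at a 20% event probability. The downside is conservatism when events are very sparse: about 1.2 to 1.5% at a 10% event probability. It also assumes that, under the null, treatment does not affect censoring.
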